12.6 Safety Follow-Up – Weeks 17-36

After the Post-Infusion Follow-Up visits are complete, subjects will return to the study site for Safety Follow-Up visits from Weeks 17 through Week 36 (\pm 48 hours), when the following procedures will be completed:

12.6.1 Once per week (Weeks 17 through 36)

Once per week from Week 17 through Week 36, the following procedures will be performed:

- Physical examination
- Assessment of Adverse Events and Concomitant Medications (including review of subject diary for bleeding and FVIII use)
- Vital Signs
- Liver Function Tests (refer to Table 9.7.8.3.1) central laboratory assessment
 - LFTs may be monitored more or less frequently (and in particular when ALT values are >1.5x ULN) based on discussion between the Medical Monitor and the Investigator and review of subject data.
- FVIII Assays central laboratory assessment
 - FVIII activity level (one-stage APTT)
 - FVIII activity level (chromogenic FXa assay)
 - FVIII coagulation activity exploratory assay
 - o Bethesda assay (with Nijmegen modification) for FVIII inhibitor level
 - FVIII antigen (ELISA)

Note: If a subject has used FVIII within 72 hours of a measurement day, all efforts should be made to obtain FVIII activity measurements when a 72-hour interval without FVIII use is achieved. The 72-hour wash-out period is only intended for subjects who have achieved FVIII \geq 5 IU/dL at 16 weeks after BMN 270 infusion and who have not resumed standard of care FVIII replacement therapy.

• Liver Function Tests (refer to Table 9.7.8.3.1) – local laboratory assessment

BOMARIN	270-201 – Amendment 6	Page 80
---------	-----------------------	---------

- LFTs may be monitored more or less frequently (and in particular when ALT values are >1.5x ULN) based on discussion between the Medical Monitor and the Investigator and review of subject data.
- FVIII activity level local laboratory assessment
 - FVIII activity level (one-stage APTT)
 - FVIII activity level (chromogenic FXa assay)

12.6.2 Once per week (Weeks 17 through 20)

Once per week from Week 17 through Week 20, the following procedures will be performed:

• PBMC collection

12.6.3 Every 2 weeks (Weeks 21 through 36)

Every 2 weeks (Weeks 22, 24, 26, 28, 30, 32, 34, and 36), the following procedures will be performed:

• PBMC collection

12.6.4 Every 4 Weeks

Every 4 weeks (Weeks 20, 24, 28, 32, and 36), the following procedures will be performed:

- Exploratory biomarker assessments
- Blood chemistry, haematology, coagulation screen, and CRP (refer to Table 9.7.8.2.1)
- Urine Tests (refer to Table 9.7.8.2.1)
- VWF:Ag
- AAV5 antibody titer
- PCR of vector DNA in blood, saliva, urine, semen, and stools
 - Sample testing during Safety Follow-Up is not required if at least
 3 consecutive samples are clear during the Post-Infusion Follow-Up period.

12.6.5 Every 8 Weeks

Every 8 weeks (Weeks 20, 28, and 36), the following procedure will be performed:

• FVIII antibody titer

12.6.6 Week 26

At Week 26, the following procedure will be performed:

• Direct Thrombin test

BOMARIN	270-201 – Amendment 6	Page 81
---------	-----------------------	---------

• Weight

12.6.7 Week 28

At Week 28, the following procedure will be performed:

• Haemo-QoL-A QoL assessment

12.7 Safety Follow-Up – Weeks 37-52

Subjects will return every 2 weeks (Week 38, 40, 42, 44, 46, 48, 50, and 52) from Week $37-52 (\pm 1 \text{ week})$, when the following procedures will be completed:

12.7.1 Once per visit

At Weeks 38, 40, 42, 44, 46, 48, 50, and 52, the following procedures will be performed:

- Physical examination
- Assessment of Adverse Events and Concomitant Medications (including review of subject diary for bleeding and FVIII use)
- Vital Signs
- Liver Function Tests (refer to Table 9.7.8.3.1) local laboratory assessment
 - LFTs may be monitored more or less frequently (and in particular when ALT values are >1.5x ULN) based on discussion between the Medical Monitor and the Investigator and review of subject data.
- FVIII activity level local laboratory assessment
 - FVIII activity level (one-stage APTT)
 - FVIII activity level (chromogenic FXa assay)
- Liver Function Tests (refer to Table 9.7.8.3.1) central laboratory assessment
 - LFTs may be monitored more or less frequently based (and in particular when ALT values are >1.5x ULN) on discussion between the Medical Monitor and the Investigator and review of subject data.
- FVIII Assays central laboratory assessment
 - FVIII activity level (one-stage APTT)
 - FVIII activity level (chromogenic FXa assay)
 - FVIII coagulation activity exploratory assay
 - o Bethesda assay (with Nijmegen modification) for FVIII inhibitor level
 - FVIII antigen (ELISA)

BOMARIN	270-201 – Amendment 6	Page 82
---------	-----------------------	---------

Note: If a subject has used FVIII within 72 hours of a measurement day, all efforts should be made to obtain FVIII activity measurements when a 72-hour interval without FVIII use is achieved; the 72-hour wash-out period is only intended for subjects who have achieved FVIII \geq 5 IU/dL at 16 weeks after BMN 270 infusion and who have not resumed standard of care FVIII replacement therapy.

12.7.2 Every 4 Weeks

Every 4 weeks (Weeks 40, 44, 48, and 52), the following procedures will be performed:

- Exploratory biomarker assessments
- Blood chemistry, haematology, coagulation screen, and CRP (refer to Table 9.7.8.2.1)
- Urine Tests (refer to Table 9.7.8.2.1)
- AAV5 antibody titer
- VWF:Ag
- PCR of vector DNA in blood, saliva, urine, semen, and stools
 - Sample testing during Safety Follow-Up is not required if at least 3 consecutive samples are clear during the Post-Infusion Follow-Up period. Subjects who have not had 3 consecutive negative samples by Week 52 should continue to have PCR testing every 4 weeks until 3 consecutive negative samples are documented (or upon consultation between the Investigator and Medical Monitor).

12.7.3 Every 8 Weeks

Every 8 weeks (Weeks 44 and 52), the following procedure will be performed:

- PBMC collection
- FVIII antibody titer

12.7.4 Week 38 and 52

At Week 38 and Week 52, the following procedure will be performed:

• Direct Thrombin test

12.7.5 Week 52

At Week 52, the following procedure will be performed:

- Haemo-QoL-A QoL assessment
- Weight

BOMARIN	270-201 – Amendment 6	Page 83
---------	-----------------------	---------

12.8 Safety Follow-Up – Years 2-5

During Years 2-5 of Safety Follow-up, the following procedures will be completed:

12.8.1 Year 2 – Every 4 Weeks

During Year 2, every 4 weeks (+ 2 weeks), the following procedures will be performed:

- Physical examination
 - Complete Physical Examination will be performed every 52 weeks; Brief Physical Examinations may be performed at other visits.
- Assessment of Adverse Events and Concomitant Medications (including review of subject diary for bleeding and FVIII use)
- Vital Signs
- Liver Function Tests (refer to Table 9.7.8.3.1) local laboratory assessment
 - LFTs may be monitored more or less frequently (and in particular when ALT values are >1.5x ULN) based on discussion between the Medical Monitor and the Investigator and review of subject data.
- FVIII activity level local laboratory assessment
 - FVIII activity level (one-stage APTT)
 - FVIII activity level (chromogenic FXa assay)
- Liver Function Tests (refer to Table 9.7.8.3.1) central laboratory assessment
 - LFTs may be monitored more or less frequently (and in particular when ALT values are >1.5x ULN) based on discussion between the Medical Monitor and the Investigator and review of subject data.
- FVIII Assays central laboratory assessment
 - FVIII activity level (one-stage APTT)
 - FVIII activity level (FXa chromogenic assay)
 - FVIII coagulation activity exploratory assay
 - o Bethesda assay (with Nijmegen modification) for FVIII inhibitor level
 - o FVIII antigen (ELISA)

Note: If a subject has used FVIII within 72 hours of a measurement day, all efforts should be made to obtain FVIII activity measurements when a 72-hour interval without FVIII use is achieved; the 72-hour wash-out period is only intended for subjects who have achieved FVIII \geq 5 IU/dL at 16 weeks after BMN 270 infusion and who have not resumed standard of care FVIII replacement therapy.

BOMARIN	270-201 – Amendment 6	Page 84
---------	-----------------------	---------

• Exploratory biomarker assessments

12.8.2 Years 3-5 – Every 6 Weeks

During Years 3-5, every 6 weeks (\pm 2 weeks), the following procedures will be performed:

- Physical examination
 - Complete Physical Examination will be performed every 52 weeks; Brief Physical Examinations may be performed at other visits.
- Assessment of Adverse Events and Concomitant Medications (including review of subject diary for bleeding and FVIII use)
- Vital Signs
- Liver Function Tests (refer to Table 9.7.8.3.1) local laboratory assessment
 - LFTs may be monitored more or less frequently (and in particular when ALT values are >1.5x ULN) based on discussion between the Medical Monitor and the Investigator and review of subject data.
- FVIII activity level local laboratory assessment
 - FVIII activity level (one-stage APTT)
 - FVIII activity level (chromogenic FXa assay)
- Liver Function Tests (refer to Table 9.7.8.3.1) central laboratory assessment
 - LFTs may be monitored more or less frequently (and in particular when ALT values are >1.5x ULN) based on discussion between the Medical Monitor and the Investigator and review of subject data.
- FVIII Assays central laboratory assessment
 - FVIII activity level (one-stage APTT)
 - FVIII activity level (FXa chromogenic assay)
 - FVIII coagulation activity exploratory assay
 - o Bethesda assay (with Nijmegen modification) for FVIII inhibitor level
 - FVIII antigen (ELISA)

Note: If a subject has used FVIII within 72 hours of a measurement day, all efforts should be made to obtain FVIII activity measurements when a 72-hour interval without FVIII use is achieved; the 72-hour wash-out period is only intended for subjects who have achieved FVIII \geq 5 IU/dL at 16 weeks after BMN 270 infusion and who have not resumed standard of care FVIII replacement therapy.

• Exploratory biomarker assessments

BOMARIN	270-201 – Amendment 6	Page 85
---------	-----------------------	---------

12.8.3 Years 2-5 – Every 3 Months

During Years 2-5, every 3 months (\pm 2 weeks), the following procedures will be performed:

- Blood chemistry, haematology, coagulation screen, and CRP (refer to Table 9.7.8.2.1)
- Urine Tests (refer to Table 9.7.8.2.1)
- AAV5 antibody titer
- FVIII antibody titer
- PBMC collection
- VWF:Ag
- Direct Thrombin test

12.8.4 Years 2-5 – Every 6 Months

Every six months starting at the Week 78 visit (ie, 26 weeks after the Week 52 visit at the end of Year 1 of the Safety Follow-up period), the following procedures will be performed:

- Haemo-QoL-A QOL assessment
- Weight

12.8.5 Years 2-5 – Every 4 Weeks

Every four weeks during Years 2-5, the following procedure may be performed:

- PCR of vector DNA in blood, saliva, urine, semen, and stools
 - Sample testing during Years 2-5 is not required if at least 3 consecutive samples are clear during the Post-Infusion Follow-Up period. Subjects who have not had 3 consecutive negative samples by Week 52 should continue to have PCR testing every 4 weeks during Years 2-5 until 3 consecutive negative samples are documented (or upon consultation between the Investigator and Medical Monitor).

12.9 Early Termination Visit

The Early Termination visit will occur on the date the subject withdraws from the study, even if the date does not correspond to a protocol-specific visit.

If a subject leaves the study prior to the Week 260 visit, the subject will be asked to return to the study site and complete an Early Termination visit. At the Early Termination visit, as many of the following assessments as possible should be done:

• Physical examination

BOMARIN	270-201 – Amendment 6	Page 86
---------	-----------------------	---------

- Assessment of Adverse Events and Concomitant Medications (including review of subject diary for bleeding and FVIII use)
- Vital Signs
- Blood chemistry, haematology, coagulation screen, and CRP (refer to Table 9.7.8.2.1)
- Urine Tests (refer to Table 9.7.8.2.1)
- Liver Function Tests (refer to Table 9.7.8.3.1) local laboratory assessment
- FVIII activity level local laboratory assessment
 - FVIII activity level (one-stage APTT)
 - FVIII activity level (chromogenic FXa assay)
- Liver Function Tests (refer to Table 9.7.8.3.1) central laboratory assessment
- FVIII Assays central laboratory assessment
 - FVIII activity level (one-stage APTT)
 - FVIII activity level (chromogenic FXa assay)
 - FVIII coagulation activity exploratory assay
 - o Bethesda assay (with Nijmegen modification) for FVIII inhibitor level
 - FVIII antigen (ELISA)

Note: If a subject has used FVIII within 72 hours of a measurement day, all efforts should be made to obtain FVIII activity measurements when a 72-hour interval without FVIII use is achieved; the 72-hour wash-out period is only intended for subjects who have achieved FVIII \geq 5 IU/dL at 16 weeks after BMN 270 infusion and who have not resumed standard of care FVIII replacement therapy.

- AAV5 antibody titer
- FVIII antibody titer
- PBMC collection
- VWF:Ag
- Direct Thrombin test
- PCR of vector DNA in blood, saliva, urine, semen, and stools
 - Sample testing at the ETV is not required if at least 3 consecutive samples are clear during the Post-Infusion Follow-Up period.
- Exploratory biomarker assessment
- Haemo-QoL-A QOL assessment

BOMARIN	270-201 – Amendment 6	Page 87
---------	-----------------------	---------

12.10 End of Study

The study will end after the last subject completes the last Safety Follow-Up visit (Week 260). BioMarin reserves the right to discontinue the study any time for clinical or administrative reasons and to discontinue participation of an individual investigator or site for clinical or administrative reasons, including, but not limited to, poor enrollment or noncompliance with procedures of the protocol or GCP. In addition, the study may be terminated if, in the opinion of BioMarin, the safety of the study subjects may be compromised.

BOMARIN	270-201 – Amendment 6	Page 88
---------	-----------------------	---------

13 DATA QUALITY ASSURANCE

BioMarin personnel or designees will visit the study site prior to initiation of the study to review with the site personnel information about the IP, protocol and other regulatory document requirements, any applicable randomization procedures, source document requirements, eCRFs, monitoring requirements, and procedures for reporting AEs, including SAEs.

At visits during and after the study, a CRA will monitor the site for compliance with regulatory documentation, with a focus on accurate and complete recording of data on eCRFs from source documents, adherence to protocol, randomization (if applicable), SAE reporting and drug accountability records.

Data quality control and analysis will be performed by BioMarin or a designee, based on a predefined analysis plan.

BOMARIN	270-201 – Amendment 6	Page 89
---------	-----------------------	---------

14 STATISTICAL METHODS AND DETERMINATION OF SAMPLE SIZE

14.1 Statistical and Analytical Plans

The statistical analysis plan (SAP) will provide additional details on the planned statistical analysis. Unless otherwise stated, all analyses will be performed using SAS.

14.1.1 Interim Analyses

No formal interim analysis is planned. An analysis of the primary endpoint will be done following all subjects having completed the study assessments through the end of the Post-Infusion Follow-Up Period (Week 16).

14.1.2 Procedures for Accounting for Missing, Unused and Spurious Data

14.2 Missing data will not be imputed.

14.3 Primary and Secondary Efficacy Analysis

The subjects will be followed in a longitudinal manner and all the relevant information will be collected. The analysis of the data will be descriptive in nature. Descriptive statistics include the number of subjects, mean, median, standard deviation, minimum, and maximum for continuous variables and count and percent for categorical variables. Efficacy variables will be summarized by dose cohort at each time point. Relationship between dose and efficacy results will be examined.

Data collected in a longitudinal manner may be analyzed using longitudinal methods such as mixed effect model which takes into account the correlation among the observation taken at various time points within a participant. Efficacy is a secondary endpoint, defined as biologically active hFVIII at \geq 5 IU/dL by chromogenic FXa and/or one-stage APTT assay as measured by the central laboratory at 16 weeks following study treatment. hFVIII activity will be assessed weekly during the study period. We can only assess the true steady state of hFVIII protein produced from BMN 270 after a minimum of 72 hours has elapsed since the last infusion of FVIII protein concentrates.

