14.7 Determination of Sample Size

No formal sample size calculations based on statistical power were performed.

The sample size is determined based upon clinical consideration and could detect a strong clinical efficacy signal. Up to 15 subjects may be dosed in the study; the actual number of subjects will depend on the criteria for dose escalation.

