Treatment of severe HA presently consists of intravenous injection of plasma derived or recombinant human FVIII protein (rhFVIII) concentrates both as prophylaxis 2-4 times per week, and at the time of a bleed, to prevent or control bleeding episodes, respectively. The half-life for FVIII (12-18 hours for most approved products) necessitates frequent infusions, and although a major advance in the treatment of HA, it remains common for severe HA patients to continue to have multiple bleeding events on treatment (mean of 1 to 7 episodes/year with prophylaxis and up to 30 to 50 episodes/year for on demand treatment) (Nagel, 2011, Haemophilia.). The consequence of multiple bleeding events is the development of an underlying pathology that contributes to debilitating multiple-joint arthropathy and substantially increased risk of death (Nagel, 2011, Haemophilia). Chemical modification (e.g. direct conjugation of polyethylene glycol (PEG) polymers) and bioengineering of FVIII (e.g. FVIII-Fc fusion proteins) improve half-life by approximately 50%, and thus, show promise in reduced dosing and maintaining activity levels above 1%trough (Stonebraker, 2010, Haemophilia.), (Mahlangu, 2014, Blood). However, these longer acting FVIIIs remain dependent on multiple infusions to maintain critical levels of FVIII activity in severe HA patients. There is therefore a strong unmet need for a fully preventive treatment of HA to give patients a FVIII level compatible with a normal and haemorrhage-free life.

Proprietary and Confidential

BOMARIN	270-201 – Amendment 5	Page 28
---------	-----------------------	---------

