9.2 Discussion of Study Design, Including Choice of Control Group

Study 270-201 is designed to be a first-in-man, phase 1/2 open-label, dose escalation study in patients with severe haemophilia A. Four doses of BMN 270 will be evaluated and the dose escalation decision tree for Cohorts 1-3 is summarized in Figure 9.1.1.

The decision to escalate to the next dose level will be made based on the review of safety parameters and FVIII activity by the Sponsor and the DRB.

There will be no control group. Parameters for each subject will be compared to a pre-treatment assessment of safety (liver function) and efficacy (number of bleeds, use of replacement therapy).

As AAV based treatment always leads to anti-capsid immune response, no true control group (for example with an empty AAV) is possible.

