9.3.1 Inclusion Criteria

Individuals eligible to participate in this study must meet all of the following criteria:

- 1. Males that are 18 years or older with established severe Haemophilia A as evidenced by their medical history. Patients will be considered as severe if their base FVIII level is 1 IU/dL or less
- 2. Treated/exposed to FVIII concentrates or cryoprecipitate for a minimum of 150 exposure days (EDs)
- 3. Greater or equal to 12 bleeding episodes only if on on-demand therapy over the previous 12 months. Does not apply to patients on prophylaxis
- 4. Able to sign informed consent and comply with requirements of the trial
- 5. No history of inhibitor, and results from a modified Nijmegen Bethesda assay of less than 0.6 Bethesda Units (BU) 2 consecutive occasions at least one week apart within the past 12 months
- 6. Sexually active patients must be willing to use an acceptable method of contraception such as double barrier, including hormonal contraception for at least 6 months post-treatment. After 6 months, subjects may stop contraception use only if they have had 3 consecutive negative semen samples.

BOMARIN	270-201 – Amendment 5	Page 45
---------	-----------------------	---------

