9.7.3 Secondary Efficacy Variables

Secondary efficacy measures will be the reduction in the frequency of factor replacement therapy, and reduction in the number of bleeding episodes. Subjects will be asked at each study visit to report the use of factor replacement therapy and the number of bleeding episodes since the previous visit. This information will be captured on the subject's diary or other subject records.

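### Change in bleeds is measured against prophylaxis for some subjects and on-demand therapy for others, so a pooled figure per dose cohort can reflect prior-regimen mix as well as dose

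*Protocol*

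**What the plan says.** There is no control group. Section 9.2 states: "Parameters for each subject will be compared to a pre-treatment assessment of safety (liver function) and efficacy (number of bleeds, use of replacement therapy"). Section 9.7.3 makes the secondary efficacy measures the reduction in factor use and the "reduction in the number of bleeding episodes". Section 14.3 then says: "Efficacy variables will be summarized by dose cohort at each time point. Relationship between dose and efficacy results will be examined".

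Both prior regimens are eligible, with different entry conditions for bleeding. Inclusion criterion 3 in Section 9.3.1 reads: "Greater or equal to 12 bleeding episodes only if on on-demand therapy over the previous 12 months. Does not apply to patients on prophylaxis". Section 7.3 gives the expected rates: "mean of 1 to 7 episodes/year with prophylaxis and up to 30 to 50 episodes/year for on demand treatment". Under Section 9.4.8.1, prior on-demand subjects carry on as before, while prior prophylaxis subjects stop prophylaxis on the infusion day and move to on-demand use.

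The Section 14.3 wording is from Amendment 6. The other sections are quoted from Amendment 5, because the Amendment 6 text of Sections 7 to 9 is not in the part of the document at hand. The Amendment 6 table of revisions lists no change to these provisions, so they are taken as carried over.

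**The concern.** The change score does not have the same zero for every subject. If the vector did nothing, a prior on-demand subject would be expected to show no change, and a prior prophylaxis subject, now without prophylaxis, would be expected to bleed more. If the vector worked completely, the on-demand subject could show a fall of 12 or more a year, while the prophylaxis subject could fall only by the few bleeds he had before. Counting every on-study bleed perfectly does not remove this, because the difference lies in the benchmark.

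Dose is assigned by sequential cohort, without randomization, and nothing in the text shown balances or displays prior regimen. Two doses with the same effect on bleeding could show different mean reductions because one cohort holds more prior on-demand subjects. A real dose difference could be hidden in the same way. What is at stake is the reading of any dose pattern in the bleeding results.

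**Working it through.** The protocol has no figure to reproduce: "No formal sample size calculations based on statistical power were performed". The check asks how far regimen mix alone can move a cohort's mean reduction.

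**Inputs from the protocol**
- Bleeds a year: prophylaxis, a mean of 1 to 7; on demand, up to 30 to 50 (Section 7.3). On-demand entry minimum: 12 (Section 9.3.1).
- Cohort sizes: 7 treated at 6E13 and 9 dosed in all (Amendment 4 summary of changes), so 9 − 7 = 2 at the two lower doses. The 4E13 cohort has 3, with up to 3 more (Section 9.1). 9 + 6 = 15 agrees with "Up to 15 subjects may be dosed in the study".

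**Assumptions**
- All on-demand subjects share one baseline, OD, and all prophylaxis subjects share another, PR. The midpoints of the quoted ranges are 40 and 4.
- Every subject has the same on-study bleed rate, so there is no dose effect.
- k of the n subjects in a cohort were previously on demand.

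**Formulas**
- Mean baseline = (k × OD + (n − k) × PR) / n.
- The common on-study rate cancels between cohorts, so the spurious difference = (OD − PR) × (k₁/n₁ − k₂/n₂).
- Replacing one prophylaxis subject by one on-demand subject moves a cohort mean by (OD − PR)/n.

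**Shift from one swapped subject (bleeds a year)**

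| OD v PR | n = 7 | n = 6 | n = 3 |
|---|---|---|---|
| 40 v 4 | 36/7 = 5.1 | 36/6 = 6.0 | 36/3 = 12.0 |
| 50 v 1 | 49/7 = 7.0 | 49/6 = 8.2 | 49/3 = 16.3 |
| 30 v 7 | 23/7 = 3.3 | 23/6 = 3.8 | 23/3 = 7.7 |
| 12 v 7 | 5/7 = 0.7 | 5/6 = 0.8 | 5/3 = 1.7 |

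**Worked example.** Take complete bleed prevention at both doses and baselines of 40 and 4. A cohort of 7 with one prior on-demand subject shows a mean fall of (40 + 6 × 4)/7 = 64/7 = 9.1. A cohort of 6 with three shows (3 × 40 + 3 × 4)/6 = 132/6 = 22.0. The gap of 12.9 is entirely mix. With the same split at 12 v 7 the gap is 5 × (3/6 − 1/7) = 1.8.

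**Chance imbalance.** Let k be binomial with the same on-demand share in cohorts of 7 and 6. The share is assumed; the protocol gives none.
- At 40 v 4, a spurious difference of at least 5 bleeds a year has probability 0.555, 0.584, 0.575 and 0.583 for shares of 10%, 20%, 30% and 50%. A difference of at least 10 has probability 0.24 to 0.27 for shares of 20% to 50%.
- At 30 v 7, at least 5 has probability 0.29 to 0.45 for shares of 20% to 50%.
- At 12 v 7, a difference of 5 needs one cohort wholly on demand and the other wholly on prophylaxis, so its probability is practically nil.

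Within a single prior regimen, the spurious difference in this model is zero by construction.

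**The case against.** The strongest reply is that this belongs to the SAP. Section 14.1 leaves detail to it, Section 14.9 lets it prevail over the protocol, and a summary by dose cohort does not rule out a further split. That is fair as to what may eventually be done. It does not remove the point: the own-history benchmark, the reduction measure and the by-cohort summary are all stated rules, and followed as written they mix two benchmarks.

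Other parts of the reply stand and limit the point.
- **Bleeding is not named as the dose-response variable.** A reader might infer that the protocol commits to a dose-response statement on bleeding. Section 14.3 speaks only of efficacy variables and results, and the one efficacy endpoint it defines is FVIII activity. Section 9.7 also states the dose-relationship goal in terms of FVIII activity.
- **On-study counts may already be shown.** Bleeds are reported at each visit, and efficacy variables are summarised at each time point, so by-dose displays could include on-study counts. In the worked example those would be zero in both cohorts.
- **The contrast is uncertain.** A reader might take the two regimens to differ tenfold. The ratio 40/4 = 10 sets the midpoint of an up-to figure against the midpoint of a mean. The quoted ranges allow 30/7 = 4.3 to 50/1 = 50, and at the entry minimum 12/7 is only 1.7.
- **No decision rests on it.** Escalation and cohort expansion depend on FVIII activity and safety (Sections 9.1 and 9.4.6.2), and there is no hypothesis test.

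**Conclusion.** The point holds in limited form. As written, the bleeding measure sets some subjects against on-demand therapy and others against prophylaxis that has since stopped. A pooled change per dose cohort can therefore reflect prior-regimen mix as well as dose.

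The size is conditional. One swapped subject moves a cohort mean by 5 to 12 bleeds a year at assumed baselines of 40 v 4, and by less than 1 in cohorts of 6 or 7 at 12 v 7. The probabilities above also depend on an assumed on-demand share.

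A reader might conclude that the bleeding results by dose are in fact confounded, or that dose selection was distorted. The documents support neither. They give no regimen mix for any cohort, so confounding is possible but not shown, and dose decisions do not use bleed counts. The issue is interpretation of a descriptive secondary endpoint, with no bearing on error rates or on FVIII activity. It is worth correcting because the better display is nearly free.

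**What to change.** In Sections 9.7.3 and 14.3, or in the SAP:
- Report change from pre-treatment bleeding separately for prior on-demand and prior prophylaxis subjects within each dose, labelled as change versus on-demand therapy and change versus prophylaxis. Do not pool the two.
- Use the on-study annualised bleed rate, rather than the reduction, as the quantity compared between doses.
- Show each subject's prior regimen in the by-dose display.

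This is a wording change. Bleeding history and FVIII usage are already documented at screening (Section 12.2), so no new data are needed. The downside is smaller cells: with at most 15 subjects, some dose-by-regimen cells may hold one subject or none, and the by-subject display will carry most of the information.
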